#### **7.2.4 Visit 3- Follow-up for possible side-effects**

The patient will be contacted by phone to record any possible side-effects they may have experienced since the removal of the patch.

### **7.3 Duration of Participation**

Patient will remain in the study until the final follow-up phone call has been made (7 days

following removal of the patch).

#### **7.4 Test Article(s) (Study Drug(s) and/or Study Device(s))**

##### **7.4.1 Description**

Granisetron transdermal delivery system - Sancuso®

##### **7.4.2 Treatment Regimen**

Study Subjects will receive one patch and it will be applied to the upper arm. The patch will stay in place for 120 hours postoperatively.

##### **7.4.3 Method for Assigning Subject to Treatment Groups**

This is an open label study –all study participants will be receiving the patch with the actual medication.

##### **7.4.4 Subject Compliance Monitoring**

The presence of the undamaged patch will be confirmed the day of surgery and at the time of discharge.

##### **7.4.5 Blinding of the Test Article**

Not applicable

##### **7.4.6 Receiving, Storage, Dispensing and Return**

###### **7.4.6.1 Receipt of Test Article**

Patches will be obtained from ProStrakan, LTD. and delivered to the Investigational Pharmacy at Hershey Medical Center.

###### **7.4.6.2 Storage**

Stability studies with 15 cm^2 Sancuso ® patches made at the development site, stored for 6 months at 40°C/75% relative humidity (RH) and for 36 months at 25°C/60% RH have been completed. Stability studies with 52 cm^2 Sancuso ® patches, made at the development site, using the same adhesive matrix formulation and stored for 24 months at 25°C/60% RH have been completed. Stability studies with 52 cm^2 Sancuso ® patches, made at the commercial manufacturing site, using the same adhesive matrix formulation and the proposed commercial format have been completed, having reached 6 months storage at 40°C/75% RH and 36 months storage at 25°C/60% and 30°C/65% RH.

Taking into account the stability data available, a shelf life of 36 months is assigned to the finished product. Each individual Sancuso ® patch is supplied in a pouch; it is recommended to store pouches at or below 25°C and out of direct sunlight, although labels for product supplied in the US will currently include the statement “Store at 20 - 25°C (68°-77°F); excursions permitted between 15°- 30°C (59°- 86°F). [See United States Pharmacopeia (USP) Controlled Room Temperature]”.

###### **7.4.6.3 Preparation and Dispensing**

Upon enrollment, the PI will write a prescription for the patch and that will be faxed to the pharmacy. The pharmacy will assign a patch to the patient and a member of the research team will pick that up from the pharmacy and deliver it to the anesthesiologist (research team member). The provider will then educate the patient on how to apply the patch to the upper arm

area. The patient will have the opportunity to practice applying the patch using a placebo patch (supplied by the sponsor). The patient will then take the patch home and apply at minimum 24 – 48 hours before surgery as hours (no longer than 48 hours) before surgery.

#### **7.4.6.4 Return or Destruction of the Test Article**

The test article will be disposed by the patient to regular waste

#### **7.4.6.5 Prior and Concomitant Therapy**

Patient will be on no antiemetic medication at the time of enrollment. After application of the patch each patient will obtain standard PONV prophylaxis in OR consisting of IV dexamethasone 4 mg. and diphenhydramine 25 mg IV. The first line rescue medication will be **Promethazine** IV 6.25 mg as per current standard of care. Promethazine will be used as slow infusion bolus (over 5-10 min) in large, good flowing peripheral IV. If this line of rescue medication does not work the patient will receive ondansetron 4 mg IV.

### **8.0 Data and Specimen Banking For Future Undetermined Research**

Not applicable

### **9.0 Statistical Plan**

#### **9.1 Sample size determination**

We are planning an open label study of cases treated with granisetron patch (no comparison group, historical control group). Prior data indicate that the failure rate (at least 1 x PONV postoperatively or administration of additional antiemetics) among patients with severe PONV is 0.85. If the true failure rate for experimental subjects is 0.4 (decrease of incidence of PONV by half), we will need to study 60 experimental subjects to be able to reject the null hypothesis that the failure rates for experimental subjects is equal to historical control with probability (power) 0.8. The Type I error probability associated with this test of this null hypothesis is 0.05. We will use an uncorrected chi-squared statistic to evaluate this null hypothesis.

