## **1.0 Objectives**

### **1.1 Study Objectives**

The objective of the study is to evaluate the efficacy and safety of adding transdermal preparation of granisetron (Sancuso ®) to the current postoperative nausea and vomiting (PONV) standard prophylaxis regimen with dexamethasone and diphenhydramine in patients with the previous history of severe, particularly delayed and/or post-discharge, PONV and undergoing surgical procedure under general anesthesia.

The specific aims of the study include:

1. efficacy of the investigated therapy in prevention of PONV up to 120 hours after surgery
2. incidence and seriousness of the observed side effects
3. ability of patients to self-administer preoperatively and maintain the investigated patch during the perioperative period
4. level of satisfaction with the preoperative PONV prophylaxis.

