### **1.2 Primary Study Endpoints**

Number of complete responders (CR, defined as no nausea or vomiting/retching episodes during 120 hours postoperatively, no additional antiemetic medication up to 120 hours after surgery)

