## **2.0 Background**

### **2.1 Scientific Background and Gaps**

Postoperative nausea and vomiting (PONV) are common and distressing symptoms to patients. The general incidence of vomiting is about 30%, the incidence of nausea is about 50%, and in a subset of high-risk patients, the PONV rate can be as high as 85%. Unresolved PONV may result in prolonged post anesthesia care unit (PACU) stay and unanticipated hospital admission that result in a significant increase in overall health care costs. The goal of PONV prophylaxis is therefore to decrease the incidence of PONV and thus patient-related distress and reduce health care costs. The major shortcoming of currently used antiemetics is their relatively short duration of prophylactic activity (e.g., about 4-6 hours for all 5HT3 receptor antagonists- 5HT3RA)

requiring its repeated dosing or, for longer acting antiemetics (e.g., scopolamine patch or dexamethasone), the presence of significant side effects and limited effectiveness.

It was reported previously that IV granisetron could be more effective than other 5HT3RA antiemetics because of its unique metabolic pathways and stronger 5HT3 receptor affinity. It is therefore important to investigate if the administration of granisetron in the prolonged activity formulation will provide effective antiemetic prophylaxis beyond 24-48 hours after administration.

It is proposed that the non-invasive patch application could extend the available repertoire of the current 5HT3RAs oral or IV regimens in PONV. Sancuso® was approved by the United States (US) Food and Drug Administration (FDA) in September 2008, and is indicated for the prevention of nausea and vomiting in patients receiving moderately and/or highly emetogenic (HE) chemotherapy regimens of up to 5 consecutive days' duration. The present study will evaluate its effectiveness in the prophylaxis of PONV.

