### **4.4 Eligibility/screening of subjects**

A detailed PONV history will be used to determine occurrence/severity of previous PONV during patient's history and physical evaluation in the Clinic (as it is done anyway for all surgical patients seen in APEC). In general the eligible patients experienced 1 or more episode of PONV with general anesthesia requiring additional treatment in PACU or had episodes of PONV after discharge from PACU or discharge from hospital.

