#### **7.2.3 Visit 3- Day of Surgery**

Patient will arrive for surgery. A member of the research team will meet them in the SDU and record the time that the patch was applied, and if it has been placed correctly, intact and still in place. Any potential side effects (systemic or local) will be recorded at that time. The subsequent standardized general anesthesia protocol for elective surgery will include general endotracheal anesthesia with sevofluran (no nitrous oxide), muscle relaxants (with reversal), intraoperative IV opioid analgesics, including standard PONV prophylaxis (dexamethasone and [diphenhydramine 25 mg IV](#) ).

Early postoperative evaluation will include recording of incidence and severity of PONV at the time of discharge from PACU (acute PONV). The incidence of vomiting or retching will be recorded by the nursing staff. Patients with symptoms requiring a rescue antiemetic—nausea score  $\geq 4$  on an 11-point Numeric Rating Scale (NRS), retching or vomiting, or patient request—within 6 hours of PACU admission will be given the first line rescue medication promethazine IV 6.25mg as per current standard of care. Promethazine will be used as slow infusion bolus (over 5-10 min) in large, good flowing peripheral IV. If the first line rescue medication does not work the patient will be given ondansetron 4 mg IV). The NRS is an 11-point linear scale on which patients rate their nausea, with 0 meaning no nausea and 10 meaning the worst possible nausea.

The subsequent evaluations will be performed either at the patient's bed (if in the hospital) or by phone call at 120 hrs (delayed or post discharge PONV). The patient will be supplied with a diary to record the information that will be requested on the follow-up phone calls.

The primary efficacy endpoint will be complete response (CR), defined as no emetic episode and no rescue medication; the proportions of patients with no emesis and no additional rescue medication in the 120 hours following the completion of surgical procedure and the change from baseline nausea score using the NRS. Treatment-emergent adverse events (TEAEs), regardless of suspected causal relationship to the study medication, will be also recorded throughout and continued until 5 days after surgery.

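### The single-arm test in section 9.1 uses an unsourced failure rate of 0.85 not tied to the background regimen, the 120-hour window or one endpoint definition, so rejecting it does not by itself answer the add-on question

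*Combined protocol and SAP*

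**What the plan says.** - **Objective (section 1.1).** The patch is studied as an addition to the "standard prophylaxis regimen with dexamethasone and diphenhydramine".
- **Treatment.** Section 7.4.3 says "all study participants will be receiving the patch with the actual medication", and section 7.4.6.5 says "each patient will obtain standard PONV prophylaxis in OR". No patient receives the two drugs without the patch.
- **Null rate (section 9.1).** "Prior data indicate that the failure rate (at least 1 x PONV postoperatively or administration of additional antiemetics) among patients with severe PONV" is 0.85. The target is 0.40, with 60 patients, power 0.8, type I error 0.05 and an uncorrected chi-squared statistic. Section 9.2 repeats only the error rate and the test. Section 9.1 states openly that there is no comparison group and that the control is historical.
- **The other 85% (section 2.1).** "in a subset of high-risk patients, the PONV rate can be as high as 85" per cent, with no citation, regimen or window.
- **Population (section 4.4).** "eligible patients experienced 1 or more episode of PONV with general anesthesia requiring additional treatment in PACU", or had PONV after leaving the PACU or the hospital.
- **Primary endpoint.** Section 1.2 requires "no nausea or vomiting/retching episodes during 120 hours postoperatively" and no additional antiemetic. Section 7.2.3 gives "complete response (CR), defined as no emetic episode and no rescue medication", and names the change in nausea score separately.

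**The concern.** To answer the add-on question from one arm, the observed failure rate must be set against the rate these patients would have on dexamethasone plus diphenhydramine alone, over 0 to 120 hours, on the same definition of failure. The documents never give that rate, and nothing shows that 0.85 is it. If the true background is lower, the test can reject although the patch contributes nothing. If it is higher, the test is harder to pass than intended.

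The endpoint conflict adds to this. The failure definition in section 9.1 counts any PONV, so it includes nausea, as section 1.2 does (section 9.1 gives no window). The definition in section 7.2.3 leaves out nausea that was not treated. Which rate is tested, and against what, is therefore not settled.

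**Working it through.** **Inputs from the documents:** n = 60 evaluable (sections 9.1 and 16.0), null 0.85, target 0.40, two-sided 5% uncorrected chi-squared test. **Assumed, because the documents give none:** background failure rates of 0.90 to 0.70 and, for the second reading, the size of the historical group.

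**The plan's own figure.** A one-sample calculation gives n = [(1.96·√(0.85·0.15) + 0.84·√(0.40·0.60)) / 0.45]² = 6.1, so 7. A two-group 1:1 calculation gives 17 per group. Neither reproduces 60. The present point does not depend on that; it takes 60 as given.

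**Reading A: 0.85 is a fixed null.** The statistic is (x/60 − 0.85)² / (0.85·0.15/60), compared with 3.84.
- x = 45: 0.0100/0.002125 = 4.71, p = 0.030, reject.
- x = 46: 0.00694/0.002125 = 3.27, p = 0.071, do not reject.

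Benefit is declared at 45 or fewer failures. If the patch adds nothing, the chance of this is P(X ≤ 45) with X binomial(60, background):

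| Assumed background | P(benefit declared, no patch effect) |
|---|---|
| 0.90 | 0.1% |
| 0.85 | 2.9% |
| 0.80 | 20.7% |
| 0.75 | 54.9% |
| 0.70 | 83.8% |

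**Reading B: 0.85 is the observed rate in a historical group.** The wording of section 9.1 also fits this. Pooled two-sample uncorrected chi-squared test:

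| Assumed group size | Cut-off (failures of 60) | P(pass), background 0.75 | P(pass), background 0.70 |
|---|---|---|---|
| 20 | 36 | 0.8% | 6.3% |
| 60 | 42 | 22.5% | 54.9% |
| 100 | 43 | 32.0% | 65.8% |
| 200 | 44 | 43.1% | 75.6% |

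**Which results are ambiguous.** Exact (Clopper-Pearson) 95% intervals:
- 24/60 (the planned 0.40): 0.276 to 0.535
- 34/60: 0.432 to 0.694
- 35/60: 0.449 to 0.709
- 44/60: 0.603 to 0.839
- 45/60: 0.621 to 0.853

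Under reading A, results of 35 to 45 failures reject 0.85 but leave a background of 0.70 inside the interval. At a true rate of 0.40, the chance of 35 or more failures is 0.3%.

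**Endpoint conflict.** Failure rate under 7.2.3 = failure rate under 1.2 − share of patients with nausea only and no rescue. That share cannot be negative, so testing the 7.2.3 endpoint against a 0.85 that counts nausea can only favour rejection. Section 7.2.3 ties rescue to a nausea score of at least 4, retching or vomiting, or patient request, so milder nausea may go untreated. The documents give no share. Assumed shares of 5% and 10% would turn 0.85 into 0.80 and 0.75, which are rows three and four of the first table.

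**The case against.** - **The limits are disclosed.** Section 7.1 calls the study an open-label pilot, section 9.1 states the historical control, and sections 13.1 and 13.2 speak cautiously of benefit. This stands as mitigation. No passage says that a rejection will be presented as proof of an add-on effect. But section 1.1 sets an add-on objective, section 9.1 plans a formal test, and nothing limits what a rejection may be taken to show.
- **The background could be 0.85 or higher.** Selection for previous severe PONV, counting any nausea and a 120-hour window could all raise it. Two prophylactic drugs, and admission after a single past episode, could lower it. This stands: the direction cannot be settled from the documents. A reader might infer that 0.85 is too high, or that the test is tilted towards benefit. The documents do not support either; the percentages above are sensitivity values, not estimates.
- **The planned effect is far from the problem zone.** This stands too. A reader might infer that no result of this trial could be informative, but 24/60 would exclude every background of 0.55 or more. The risk lies in intermediate results, which arise mainly if the patch works much less well than planned.
- **The endpoint conflict is a separate matter.** It is an inconsistency in its own right, but the null rate cannot be justified until the definition it refers to is fixed.

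**Conclusion.** The point holds as a gap in justification and interpretation. Nothing ties 0.85 to the two-drug regimen alone, to 0 to 120 hours or to the eligible population, so rejecting it does not by itself answer the question in section 1.1. With 0.85 as a fixed null, the chance that a patch adding nothing passes runs from 0.1% to 83.8% over assumed backgrounds of 0.90 to 0.70. With a small historical group it is much lower. These figures rest on assumed backgrounds and on 60 evaluable patients. The contradiction between sections 1.2 and 7.2.3 is certain from the text; its size is not known, but its direction against a nausea-inclusive 0.85 is towards rejection. It should be fixed, but the trial can still run as a pilot.

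**What to change.** 1. **Endpoint.** Reconcile sections 1.2, 7.2.3 and 9.1 to one definition of failure and one window, and use a null rate on that same definition.
2. **Section 9.1.** State whether 0.85 is a fixed null or the rate in a historical sample (with its size), and give its source, background prophylaxis and time window.
3. **Section 9.2.** Make the failure rate with its exact 95% interval the main result, and add wording such as: an effect of adding the patch will be claimed only relative to background failure rates above the upper limit of this interval. State that the comparison is non-concurrent and open label, with patient-reported nausea.
4. **Interval and test together.** The interval may take precedence over the chi-squared test only if 0.85 is a fixed null; there they differ only at 45/60, where p = 0.030 but the interval reaches 0.853. If 0.85 comes from a historical sample, its sampling error must be carried, and a claim against it must also pass the two-sample test. Otherwise the rule would be looser than planned: the exact interval excludes 0.85 up to 44/60, against cut-offs of 36, 42 and 43 for groups of 20, 60 and 100.

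**Cost.** Wording, some work to source a matched rate, and a more modest conclusion; no added patients. At a true failure rate of 0.40, the interval from 60 patients would exclude a known background of 0.70 with probability 99.7%, 0.60 with 82%, and 0.55 with only 56%.

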#### **9.2 Statistical methods**

The Type I error probability associated with this test of this null hypothesis is 0.05. We will use an uncorrected chi-squared statistic to evaluate this null hypothesis.

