## 16.0 Number of Subjects

We require 60 evaluable patients, with an enrollment of up to 80 patients which would include a potential of 20 screen failures.

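### Section 9.1's 60 subjects at 80% power do not follow from its own inputs: 0.85 versus 0.40 needs about 6 to 10 patients, and 60 give power above 99.99%

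*Combined protocol and SAP*

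**What the plan says.** Section 9.1 describes an open-label study with "no comparison group, historical control group". The historical failure rate "among patients with severe PONV is 0.85". The alternative reads "If the true failure rate for experimental subjects is 0.4 (decrease of incidence of PONV by half"). From this the section concludes that "we will need to study 60 experimental subjects to be able to reject the null hypothesis" "with probability (power) 0.8". It adds: "The Type I error probability associated with this test of this null hypothesis is 0.05".

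Section 9.2 repeats the type I error and the test and goes no further: "We will use an uncorrected chi-squared statistic to evaluate this null hypothesis". Section 16.0 says "We require 60 evaluable patients" and allows enrolment of up to 80 to cover 20 screen failures.

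The documents do not say whether the test is one-sided or two-sided, give no size for the historical group, and offer no precision, safety or feasibility reason for 60.

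**The concern.** A drop from 0.85 to 0.40 is very large, and a few patients are enough to detect it. Sixty is many times the number that the stated inputs imply, so either the number or the power attached to it is wrong.

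What is at stake is interpretation. Section 9.1 ties 60 patients to a halving of PONV at 80% power. A reader would take a significant result as evidence of an effect of roughly that size. If 60 patients give far more power than stated, the test also rejects for much smaller reductions. Section 9.2 asks for no estimate or interval that would show the difference. The study is open label with no concurrent control, so a small departure from an external benchmark is weak evidence in any case.

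**Working it through.** **Inputs (section 9.1).** p0 = 0.85, p1 = 0.40, difference 0.45, alpha 0.05, power 0.80, uncorrected chi-squared. Sidedness is not stated. The null is one of equality, so two-sided is taken as the main case: z = 1.960 for alpha and 0.842 for power.

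**Attempt to reproduce 60**

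*One-sample test against a fixed 0.85* (the plan has no comparison group):

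n = [(1.960 × √(0.85 × 0.15) + 0.842 × √(0.40 × 0.60)) / 0.45]²
= [(1.960 × 0.3571 + 0.842 × 0.4899) / 0.45]² = 6.1, so 7 patients. One-sided, it is 4.9, so 5.

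The approximation is rough at this size. With an exact binomial test at 0.025 per tail, power is 71.0% at n = 7, 82.6% at n = 8, 73.3% at n = 9 and 83.4% at n = 10. The exact answer is therefore 8 to 10.

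*Two-sample test, equal groups,* mean rate 0.625:

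n per group = [(1.960 × √(2 × 0.625 × 0.375) + 0.842 × √(0.85 × 0.15 + 0.40 × 0.60)) / 0.45]² = 16.9, so 17 per group. One-sided, 14.

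*Other routes to 60*

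| Reading | Result |
|---|---|
| 60 as a total of 30 + 30, two-sample | power about 97% |
| Exact halving, 0.425 instead of 0.40 | at most 11 one-sample, 24 per group two-sample |
| 60 treated against 10 historical controls | power about 82% |
| 60 treated against 8 historical controls | power 72% to 75%, depending on method |
| Allowance for attrition | ruled out: section 16.0's 60 are already evaluable patients |

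Only a historical group of about 10 patients brings 60 treated subjects near 80% power. The documents mention no such group, so this is not a reproduction.

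**What 60 patients actually give (one-sample, two-sided)**

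The standard error under the null is √(0.85 × 0.15 / 60) = 0.0461.

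| Failures | Rate | z | p |
|---|---|---|---|
| 45/60 | 75.0% | (0.750 − 0.850)/0.0461 = −2.17 | 0.030 |
| 46/60 | 76.7% | −1.81 | 0.071 |

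The test rejects at 45 or fewer failures, or at 57 or more. Its actual type I error is 0.0291 + 0.0148 = 0.044.

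| True failure rate | Exact power |
|---|---|
| 0.40 | 1 − 8 × 10⁻⁹ |
| 0.70 | 83.8% |
| 0.71 | 79.3% |

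So 80% power belongs to a true rate of about 0.71, not 0.40. Against 60 historical controls, power at 0.40 is still about 99.97% to 99.98%, and 80% power falls at a true rate of about 0.63.

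**What the boundary result would mean.** At 45/60 there are 15/60 = 25% complete responders. The exact 95% interval for the failure rate is 62.1% to 85.3%, well above 0.40. Its upper limit also just includes 0.85 although the chi-squared test rejects, so the two methods can disagree at the boundary.

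**The case against.** Five points can be made for the plan.

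- **The 75% boundary depends on a fixed benchmark.** Section 9.1 also speaks of a historical control group. Against 60 controls with 51 failures (85%), the largest significant count is 42/60 (70%), and 45/60 gives z = −1.37. This is correct, but the plan supplies only the value 0.85 and no historical sample size, so the one-sample test is the only one that can be run as written. Non-reproduction of 60 holds on either reading.
- **Any well-powered test rejects at observed effects smaller than the design alternative,** and the plan nowhere says that rejection proves halving. Also correct. The assumed rate of 0.40 is not shown to be wrong either. What is wrong is the link between 60, 0.40 and 80% power, and the gap here is wide: a 10-point fall against a planned 45.
- **The error is on the safe side.** The type I error is not inflated and the primary test is not underpowered. For a pilot that also looks at side effects, patch self-administration and satisfaction, 60 may be sensible. That softens the consequence, but the plan does not offer this reason.
- **The benchmark is itself soft.** Section 2.1 gives 85% as the upper end for a high-risk subset. This stands, and makes bare rejection of 0.85 less informative still.
- **The endpoint should be settled first.** Section 1.2 requires absence of nausea for a complete response, while section 7.2.3 defines it by emesis and rescue use only. Restated power figures apply only to an endpoint for which 0.85 is the right benchmark. This is a fair condition on the correction and does not explain 60.

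**Conclusion.** The concern holds. On section 9.1's own inputs the required number is about 6 to 10 patients one-sample, or 17 per group against an equal-sized historical group. With 60 evaluable patients the power at a true rate of 0.40 is above 99.99% (one-sample), not 80%. The one-sample figures of 0.71 for 80% power and 45/60 for the rejection boundary assume 0.85 is a known constant and the test is two-sided at 0.05. With a finite historical group they move (about 0.63 and 42/60 with 60 controls), and the conclusion does not change. This is the plan's only justification for its sample size and should be corrected. The number of patients need not change.

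**What to change.** Keep 60 evaluable patients and rewrite the text.

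**Section 9.1** should state:
- a one-sample, two-sided, uncorrected chi-squared test of the failure rate against a fixed 0.85, at alpha 0.05;
- power above 99.9% if the true rate is 0.40, and about 80% if it is about 0.71;
- rejection in favour of the patch at 45 or fewer failures in 60 (75%);
- the reason for 60 as precision and feasibility: at 40% failure the 95% interval has a half-width of 1.96 × √(0.40 × 0.60 / 60) = 0.124, about 12 points (exact interval for 24/60: 27.6% to 53.5%).

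If a real historical dataset is to be the comparator, give its source and size and redo these figures as a two-sample test.

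**Section 9.2** should state that the failure rate will be reported with its exact 95% confidence interval, that rejecting 0.85 alone does not show a halving, and that any such claim rests on the estimate and interval. It should also say whether the test or the exact interval governs if they disagree, as they do at 45/60.

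Settle the definition of complete response between sections 1.2 and 7.2.3 before the figures are finalised.

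The cost is wording in 9.1 and 9.2, with no added patients or data collection. The one drawback is that the stated rationale for 60 changes.
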